Revised Clinical Study Protocol

Drug Substance TC-5214
Study Code D4130C00008
Edition Number 1
Date [REDACTED]

An Open-Label, Multi-Center, Phase I Study To Compare the Pharmacokinetics of a Single Oral Dose of TC-5214 (S-Mecamylamine) in Subjects with Renal Impairment with Subjects with Normal Renal Function

Sponsor: AstraZeneca [REDACTED]

AstraZeneca Research and Development site representative

[REDACTED]

[REDACTED]

Date

This submission /document contains trade secrets and confidential commercial information, disclosure of which is prohibited without providing advance notice to AstraZeneca and opportunity to object.

The following Amendment(s) and Administrative Changes are included in this revised protocol:

Amendment No.	Date of Amendment	Local Amendment No.	Date of local Amendment
1	[REDACTED]		
Administrative change No.	Date of Administrative Change	Local Administrative change No.	Date of local Administrative Change

[REDACTED]

PROTOCOL SYNOPSIS

An Open-Label, Multi-Center, Phase I Study To Compare the Pharmacokinetics of a Single Oral Dose of TC-5214 (S-Mecamylamine) in Subjects with Renal Impairment with Subjects with Normal Renal Function

Coordinating Principal Investigator

[REDACTED]

Study center(s) and number of subjects planned

The study will be a multi-center study conducted at up to 3 centers in the United States. Eight subjects in each category of mild, moderate renal impairment, end stage renal disease requiring dialysis, and 8 male or female subjects without renal impairment will be dosed for a total of approximately 32 evaluable subjects to complete the study.

Study period		Phase of development
Estimated date of first subject enrolled	[REDACTED]	Phase 1
Estimated date of last subject completed	[REDACTED]	

Primary Objective

To assess the pharmacokinetics of a single dose of TC-5214 in subjects with renal impairment and to compare the results with those in subjects with normal renal function

Secondary Objective

- To assess the effect of hemodialysis on TC-5214 pharmacokinetics
- To assess the safety and tolerability of TC-5214 in subjects with renal impairment compared with those subjects with normal renal function

Exploratory Objectives

To collect samples for potential pharmacogenetic testing, which will allow future investigation of the influence of genotype on drug disposition and pharmacodynamic response

Study design

This is a Phase I single dose, multi-center, open-label study designed to evaluate the safety, tolerability and pharmacokinetics of TC-5214 in renally impaired subjects compared with subjects with normal renal function.

Based on an interim review of the safety and pharmacokinetics data, subjects with severe renal impairment (previous Group 4) will not be recruited for this study, and the study will be conducted in 2 parts.

Subjects will be enrolled into 1 of 4 groups in parallel, according to their degree of renal impairment based on their estimated glomerular filtration rate (eGFR), determined using the abbreviated, 4-variable Modification of Diet in Renal Disease formula as follows:

Group 1: control subjects with normal renal function: eGFR greater than 80 mL/min

Group 2: mild renal impairment: eGFR greater than or equal to 50 to 80 mL/min

Group 3: moderate renal impairment: eGFR greater than or equal to 30 to less than 50 mL/min

Group 5: end stage renal disease: eGFR less than 30 mL/min, currently receiving dialysis

Part 1, Groups 1 through 3:

Subjects in Groups 1 through 3 will not be on dialysis. They will be admitted to the clinic the morning of Day -1, or on Day -2 at the discretion of the Investigator. Time-matched vital signs will be collected on Day -1. Subjects will then receive a single oral dose of TC-5214 on Day 1 and will remain in the clinic until the completion of the study assessments and procedures scheduled on Day 4. Subjects will return to the clinic for a follow-up visit 7 to 10 days following discharge from the clinic. Subjects in Group 1 who withdraw from the study prior to completion of all PK sample collections may be replaced; subjects in Groups 2 and 3 who withdraw from the study prior to completion of all PK sample collections may be replaced to ensure a minimum of 6 subjects complete the treatment period. During Part 1, subjects in Groups 1 through 3 will have pharmacokinetic blood and urine samples collected through 72 hours postdose.

Part 1, Group 5:

The first 4 subjects enrolled into Group 5 will participate in 2 treatment periods, and receive a single oral dose of TC-5214 on each occasion. For Treatment Period 1 subjects will be admitted into the clinic the morning of Day -1, or on Day -2 at the discretion of the Investigator. Time-matched vital signs will be collected on Day -1. Subjects will receive a single dose of TC-5214 on Day 1 after completion of a dialysis session and will remain in the

clinic for pharmacokinetic sample collections and safety assessments until the start of their next dialysis session. Subjects who are unable to remain in the clinic during this time may have their samples collected as outpatients. Subjects will return to the clinic after a washout period of at least 2 weeks to start Treatment Period 2. Subjects will be admitted to the clinic the morning of Day -1 or on Day -2 at the discretion of the Investigator for Treatment Period 2. Time-matched vital signs will be collected on Day -1. Subjects in Treatment Period 2 will receive a single dose of TC-5214 on Day 1, at 4 hours prior to the start of a dialysis session. Subjects will remain in the clinic until the start of their next dialysis session. Blood samples will be collected prior to dialysis, during the entire dialysis session, and until the start of their next dialysis session. Safety assessments will be performed periodically throughout the treatment period. Dialysis fluid will be collected in 1-hour intervals. Subjects who are unable to remain in the clinic through the entire treatment period may have their samples collected as outpatients. Subjects will return to the clinic for a follow-up visit 7 to 10 days following discharge from Treatment Period 2. Subjects who withdraw from the study after completion of Treatment Period 1 (assessments between dialysis) and before entering Treatment Period 2 (assessments during dialysis) may be replaced at the discretion of the Sponsor.

Part 2, Groups 1 through 3:

Subjects in Groups 1 through 3 will not be on dialysis. They will be admitted to the clinic the morning of Day -1, or on Day -2 at the discretion of the Investigator. Time-matched vital signs will be collected on Day -1. Subjects will then receive a single oral dose of TC-5214 on Day 1 and will remain in the clinic until the completion of the study assessments and procedures scheduled on Day 6. Subjects will return to the clinic for a follow-up visit 7 to 10 days following discharge from the clinic. Subjects in Group 1 who withdraw from the study prior to completion of all PK sample collections may be replaced; subjects in Groups 2 and 3 who withdraw from the study prior to completion of all PK sample collections may be replaced to ensure a minimum of 6 subjects complete the treatment period.

During Part 2, subjects in Groups 1 through 3 will have blood and urine samples collected through 120 hours postdose.

Part 2, Group 5:

The remainder of subjects enrolled into Group 5 will participate in 1 treatment period, and receive a single oral dose of TC-5214. They will be admitted to the clinic the morning of Day -1, or on Day -2 at the discretion of the Investigator. Time-matched vital signs will be collected on Day -1. Subjects will then receive a single oral dose of TC-5214 on Day 1 after completion of their first inpatient dialysis session, and will remain in the clinic until the completion of the study assessments and procedures scheduled on Day 6.

Pharmacokinetic blood samples will be collected after a single oral dose (Day 1) for up to 120 hours postdose. Samples will be collected through 72 hours postdose (assessment between dialysis) and between 72 and 120 hours (assessment during dialysis). Pharmacokinetic urine samples will be collected for up to 120 hours postdose from subjects who are able to produce urine.

Subjects will return to the clinic for a follow-up visit 7 to 10 days following discharge from the clinic. Subjects who withdraw from the study prior to completion of all pharmacokinetic sample collections may be replaced at the discretion of the Sponsor.

Target subject population

The target population will include male and female nonpregnant, nonlactating subjects with normal, and mild, moderate, and end stage renal impairment on dialysis, aged 18 to 80 years with a body mass index between 19 and 40 kg/m². The demographics of healthy subjects with normal renal function will be matched for age \pm 10 years, and body mass index \pm 3 kg/m², to the mean age and body mass index of subjects across the 3 renal impairment groups. Sex will be matched to achieve similar distribution between male and female subjects.

Investigational product, dosage and mode of administration

TC-5214 will be administered orally with 240 mL of water on Day 1. All subjects in Groups 1 and 2 will receive a single oral dose of 8 mg TC-5214 on 1 occasion. All subjects in Groups 3-4 will receive a single oral dose of 2 mg TC-5214 on 1 occasion. Subjects in Groups 5 will receive a single oral dose of 2 mg TC-5214 on 2 occasions separated by an at least 2 week washout period.

Duration of treatment

For Groups 1 through 3 the duration of each subject's participation will be approximately 47 days, including a screening period of up to 30 days, a treatment period consisting of 6 to 7 nights (depending on the admission day) and a follow-up visit, 7 to 10 days after discharge from the treatment period.

For the first 4 subjects in Group 5 (Part 1) participating in the 2-period portion of the study, duration of each subject's participation will be approximately 55 days. These subjects will be given the option to remain at the clinic between samplings for the off dialysis assessment (post dialysis dosing) at the discretion of the Investigator.

For the remaining subjects in Group 5 (Part 2) participating in a single treatment period, duration of each subject's participation will be approximately 47 days.

Subjects may be admitted to the clinic on Day -2 for the Day -1 assessments at the discretion of the Investigator.

Outcome variable(s):

- Pharmacokinetic
 - Primary plasma pharmacokinetic parameters: AUC and C_{max},
 - Secondary plasma pharmacokinetic parameters: CL/F, t_{1/2}, t_{max}, and V_z/F in all subjects; Ae, CL_D, and fe in Groups 1 to 4; A_{d(4-8)}, Cl_R, and fd₍₄₋₈₎ in Group 5 during Period 2

- **Safety**

Adverse events and serious adverse events including severity, vital signs, physical examinations, laboratory parameters, electrocardiograms, and the Columbia-Suicide Severity Rating Scale.

Statistical methods

Tabulations and listings of data for vital signs, physical examinations, clinical laboratory tests, and electrocardiograms will be presented. Results from the Columbia Suicide Severity Rating Scale will be presented separately in a listing only. For clinical laboratory tests, listings of values for each subject will be presented with abnormal or out-of-range values flagged (other than those associated with renal impairment and /or stable chronic condition). Plasma and urine concentration data and the derived pharmacokinetic parameters will be summarized by renal function group using descriptive statistics.

Regression models will be used to assess and quantify the relationship between renal function, as measured by the eGFR, and TC-5214 dose-normalized primary pharmacokinetic parameters (C_{max} and AUC). The initial model will specify a linear relationship between primary pharmacokinetic parameters and the eGFR, and will be estimated using ordinary least squares. Log-transformations may be used to improve model fit. Models which are non-linear in the model parameters will be used in the event that linear models do not yield an adequate fit. Model parameters, 90% CI and p-values will be reported. From the final models, estimates of the mean pharmacokinetic parameters and 90% CI will be made at the median eGFR of each of the renal function groups, as will the differences (or ratios) and 90% CI relative to the control subjects with normal renal function.

As an exploratory analysis, the renal function groups will be compared using a one-way analysis of variance model on the log-transformed dose-normalized primary pharmacokinetic parameters (C_{max} and AUC). The renal impairment groups will be compared to the control subjects with normal renal function (Group 1), with the latter as reference. Geometric least-squares means with corresponding 95% CI and ratios of geometric least squares with corresponding 90% CI will be presented. While this study is not statistically powered in terms of claiming no effect of renal impairment on TC-5214 exposure, interpretation of the effect of renal impairment will be based on point estimates and associated 90% confidence intervals.

Comparisons of pharmacokinetic parameters for subjects in Group 5 with endstage renal disease on a nondialysis day with those on a dialysis day will be performed using a paired t-test (C_{max} and AUC).

	PAGE
TITLE PAGE	1
PROTOCOL SYNOPSIS.....	2
TABLE OF CONTENTS.....	7
LIST OF ABBREVIATIONS AND DEFINITION OF TERMS	12
1. INTRODUCTION	15
1.1 Background	15
1.2 Research hypothesis.....	15
1.3 Rationale for conducting this study	15
1.4 Benefit/risk and ethical assessment	16
2. STUDY OBJECTIVES.....	16
2.1 Primary objective.....	16
2.2 Secondary objectives	16
2.3 Exploratory objectives	16
3. STUDY PLAN AND PROCEDURES	17
3.1 Overall study design and flow chart	17
3.1.1 Part 1	17
3.1.1.1 Part 1, Groups 1 through 3	17
3.1.1.2 Part 1, Group 5	17
3.1.2 Part 2	18
3.1.2.1 Part 2, Groups 1 through 3	18
3.1.2.2 Part 2, Group 5.....	18
3.2 Rationale for study design, doses and control groups.....	28

AE	Adverse event (see definition in Section 6.3.1)
AUC	Area under plasma concentration time curve from zero to infinity
AUC _(0-t)	Area under plasma concentration time curve from zero to last quantifiable time point
AUC ₍₄₋₈₎	Area under plasma concentration time curve from 4 to 8 hours postdose
%AUC _{ex}	Percentage of AUC obtained by extrapolation
BMI	Body Mass Index
BP	Blood pressure
CI	Confidence interval
CL/F	Apparent plasma clearance
CL _D	Dialysate clearance
Cl _R	Renal clearance
C _{max}	Maximum plasma concentration
CPA	Clinical Pharmacology Alliance
CRF	Case Report Form (electronic/paper)
CL _{CR}	Creatinine clearance
CSA	Clinical Study Agreement
CSP	Clinical Study Protocol
CSR	Clinical Study Report
C-SSRS	Columbia-Suicide Severity Rating Scale
CV%	Coefficient of variation (%)
DAE	Discontinuation of Investigational Product due to Adverse Event
DES	Data Entry Site
DMP	Data Management Plan
DMPK	Drug metabolism and pharmacokinetics
DNA	Deoxyribonucleic acid

Abbreviation or special term	Explanation
ECG	Electrocardiogram
ESRD	End stage renal disease
eCRF	Electronic case report form
eGFR	Estimated glomerular filtration rate
f_e	Fraction of dose excreted as unchanged drug into urine
$f_{d(4-8)}$	Fraction of dose extracted unchanged into the dialysate over the dialysis period from 4 hours postdose to 8 hours postdose
FSH	Follicle stimulating hormone
GCP	Good clinical practice
GMP	Good manufacturing practice
HIV	Human immunodeficiency virus
ICF	Informed Consent Form
ICH	International Conference on Harmonisation
IP	Investigational Product
IRB	Institutional Review Board
LIMS	Laboratory Information Management System
LH	Luteinizing hormone
LLOQ	Lower Limit of Quantification
MDRD	Modification of Diet in Renal Disease
OAE	Other Significant Adverse Event (see definition in Section 11.1.1)
pCRF	paper case report form
PGx	Pharmacogenetic research
PI	Principal Investigator
PK	Pharmacokinetics
PR(PQ)	ECG interval measured from the onset of the P wave to the onset of the QRS complex.
QRS	ECG interval measured from the onset of the QRS complex to the J point.
QT	ECG interval measured from the onset of the QRS complex to the end of the T wave
QTcF	QT interval corrected for heart rate using Fridericia's formula
RR	The time between corresponding points on 2 consecutive R waves on ECG
SAD	Single ascending dose
SAE	Serious adverse event (see definition in Section 6.3.2).

Abbreviation or special term	Explanation
SD	Standard deviation
SOP	Standard Operating Procedure
$t_{1/2,\lambda z}$	Terminal half-life
V_z/F	Apparent volume of distribution

1. INTRODUCTION

1.1 Background

Mecamylamine HCl (Inversine®) was originally developed as a nicotinic ganglion-blocking agent and was approved in the United States in 1956 for the treatment of moderately severe to severe essential hypertension and in uncomplicated cases of malignant hypertension. The safety and tolerability profile of Mecamylamine HCl has been established during its decades of clinical use as an antihypertensive agent. At the high doses (greater than 10 mg/day up to 90 mg/day) used in antihypertensive therapy, the most common Adverse Events (AE) of the drug include constipation, orthostatic dizziness, urinary retention, and blurred vision. At dosages of 2.5 to 10 mg/day (one-tenth of the dosages used in the treatment of hypertension) the mecamylamine antagonizes central nervous system neuronal nicotinic receptors with no effect on those in the periphery and no impact on blood pressure.

TC-5214 is the S-(+)-enantiomer of racemic mecamylamine and is the more active enantiomer. A single ascending dose (SAD) study (TC-5214-23-CLP-001) has been conducted with TC-5214 in healthy male volunteers. In this study, TC-5214 was generally well tolerated across 4 dose cohorts (single doses of 2 mg, 4 mg, 8 mg and 16 mg; 6 volunteers per cohort). There were no serious adverse events (SAEs) in the SAD study. Additionally, a Phase 2b study (TC-5214-23-CRD-001) was conducted to evaluate the efficacy and safety of TC-5214 including evaluation of the level of exposure to TC-5214 in the target patient population. In this Phase 2b study, a flexible dose titration design was used, and doses from 1 mg twice daily (2 mg total per day) through 4 mg twice daily (8 mg total per day) TC-5214 was administered to the active treatment arm. There were 2 serious adverse events (SAE) in the study: possible seizure and menorrhagia. For further details, see the Investigator's Brochure ([Investigator's Brochure TC-5214](#))

1.2 Research hypothesis

The hypothesis in this study is that renal impairment may affect the plasma pharmacokinetics (PK) of TC-5214, by decreasing the renal clearance (Cl_R) of TC-5214, leading to increased exposure.

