3.1 Overall study design and flow chart

This is a Phase I single dose, multi center, open-label study designed to evaluate the safety, tolerability and PK of TC-5214 in renally impaired subjects compared with subjects with normal renal function.

Based on an interim review of the safety and pharmacokinetics data, subjects with severe renal impairment (previous Group 4) will not be recruited for this study, and the study will be conducted in 2 parts.

Subjects will be enrolled into 1 of 4 groups in parallel, according to their degree of renal impairment based on their estimated glomerular filtration rate (eGFR), determined using the abbreviated, 4-variable Modification of Diet in Renal Disease (MDRD) formula as follows:

Group 1: control subjects with normal renal function: eGFR greater than 80 mL/min

Group 2: mild renal impairment: eGFR greater than or equal to 50 to 80 mL/min

Group 3: moderate renal impairment: eGFR greater than or equal to 30 to less than 50 mL/min

Group 5: end stage renal disease (ESRD): eGFR less than 30 mL/min, currently receiving dialysis

3.1.1 Part 1

3.1.1.1 Part 1, Groups 1 through 3

Subjects in Groups 1 through 3 will not be on dialysis. They will be admitted to the clinic the morning of Day -1, or on Day -2 at the discretion of the Investigator. Time-matched vital signs will be collected on Day -1. Subjects will then receive a single oral dose of TC-5214 on Day 1 and will remain in the clinic until the completion of the study assessments and procedures scheduled on Day 4. Subjects will return to the clinic for a follow-up visit 7 to 10 days following discharge from the clinic. Subjects in Group 1 who withdraw from the study prior to completion of all PK sample collections may be replaced; subjects in Groups 2 and 3 who withdraw from the study prior to completion of all PK sample collections may be replaced to ensure a minimum of 6 subjects complete the treatment period. During Part 1, subjects in Groups 1 through 3 will have pharmacokinetic blood and urine samples collected through 72 hours postdose.

3.1.1.2 Part 1, Group 5

The first 4 subjects enrolled into Group 5 will participate in 2 treatment periods, and receive a single oral dose of TC-5214 on each occasion. For Treatment Period 1 subjects will be

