Pharmacogenetic sampling (optional) ^k		X							6.5.1
TC-5214 administration ^d			X						5.5.2
Blood sample collection for PK ^e			X	X	X	X	X		6.4.1.1
Urine sample collection for PK ^f			X	X	X	X	X		6.4.1.2
Dialysis Period / Dialysate Collection			X ^j						6.4.1.4
Discharge from clinic							X ^g		NA

Visit number	1	2 Residential Period (For Group 5, Part 1 – 2 Residential Periods)					3		
	Activity/ Day	-30 to -2 Screening	-1 ^h	1	2	3	4	Follow-Up 7 to 10 days following discharge	Details in Section
Concomitant medications	X	X	X	X	X	X	X		5.6
Adverse Events	X	X	X	X	X	X	X		6.3

^a Height will be measured during the screening visit only.

^b Orthostatic blood pressure and pulse will be measured at the Screening Visit, on Day -1 (time to correspond with the planned predose and 4 hour postdose timings for Day 1), on Day 1 at predose and 4 hours post dose, each morning during the residential period and at the Follow-up Visit.

^c Subjects must rest in the supine position for 10 minutes prior to the 12-lead ECG evaluation to be performed at screening, on admission on Day -1, on Day 1 at 4 hours postdose, before discharge on Day 4, and at the Follow-up Visit

^d Study drug will be administered with 240 mL room temperature water

^e For detailed timings of blood PK sampling times see Section 6.4.1.1.

^f Urine collection times for Groups 1 to 3: Urine will be collected for 72 hours postdose in the following intervals: 0-12, 12-24, 24-48 and 48-72 hours.

^g Subjects will be discharged from the unit after all study procedures have been completed.

^h Subjects may be admitted to the clinic on Day -2 for the Day -1 assessments at the discretion of the Investigator.

ⁱ Abbreviated physical examination.

^j Applies only to Group 5, Part 1, Treatment Period 2. Subjects will start their scheduled dialysis at 4 hours post TC-5214 administration. Dialysate will be collected over 1 hour intervals throughout the entire (approximately 4 hour) dialysis session (eg, 0 to 1, 1 to 2, 2 to 3, and 3 to 4 hours).

^k Subjects must agree to sign a separate, optional informed consent for genetic research in order for this sample to be collected.

Table 2: Study Plan, Part 2

Visit number	1	2 Residential Period							3	
	-30 to -2 Screening	-1 ^h	1	2	3	4	5	6	Follow-Up 7 to 10 days following discharge	Details in Section
Informed consent	X									8.4
Demography	X									6.2
Inclusion/exclusion criteria	X	X								4
Physical Examination	X	X ⁱ						X ⁱ	X	6.3.6

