6.4.1.3 Urine Samples

Urine samples (approximately 10 mL in total, split into 2 tubes) for determination of concentrations of TC-5214 in urine will be taken from the total urine sample provided during each collection period presented in the study plans. The weight, volume, specific gravity, and start/stop time for each interval of each urine collection will be recorded.

For Part 1, urine will be collected in Groups 1 through 3 from predose to 72 hours postdose (see [Table 1](#)).

For Part 2, urine will be collected in Groups 1 through 3 and in Group 5 subjects who are able to produce urine from predose to 120 hours postdose (see [Table 2](#)).

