data and dose-normalized PK parameters will be presented by renal function. Figures of PK parameters will also be presented by dose. Individual subject concentration-time data will be graphically presented on linear and semi-logarithmic scales.

For Groups 1 through 3 and Group 5, (Part 1, Treatment Period 1 and Part 2), regression models will be used to assess and quantify the relationship between renal function, as measured by eGFR, and TC-5214 dose-normalized primary pharmacokinetic parameters (C_{max} and AUC). The initial model will specify a linear relationship between primary pharmacokinetic parameters and eGFR and will be estimated using ordinary least squares. Log-transformations may be used to improve model fit. Non-linear models will be used if there is statistical evidence of departure from linearity at the 0.10 significance level. Further, models which are non-linear in the model parameters may be used if simpler models do not provide adequate fit. Model parameters, 90% CI and p-values will be reported. From the linear and final models, estimates of the mean pharmacokinetic parameters and 90% CI will be made at the median eGFR of each of the renal function groups, as will the differences (or ratios) and 90% CI relative to the normal renal group (at the group median eGFR).

As an exploratory analysis, the renal function groups will be compared using a one-way analysis of variance model on the log-transformed dose-normalized primary pharmacokinetic parameters (C_{max} and AUC). The renal impairment groups will be compared to the control subjects with normal renal function (Group 1), with the latter as reference. Geometric least-squares means with corresponding 95% CI and ratios of geometric least squares with corresponding 90% CI will be presented.

Comparisons of PK parameters for subjects in Group 5, Part 1, with ESRD between the two treatment periods (ie on a non dialysis day with those on a dialysis day) will be performed using a paired t-test (C_{max} and AUC).

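### Renal clearance, the mechanism named in the hypothesis, is derived and tabulated but has no planned model against eGFR and no ratio to controls; the synopsis also transposes it with dialysate clearance

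*Supplement*

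**What the plan says.** The hypothesis in Section 1.2 is that "renal impairment may affect the plasma pharmacokinetics (PK) of TC-5214, by decreasing the renal clearance"; the sentence goes on to name higher exposure as the consequence.

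Section 12.2.3 states that "regression models will be used to assess and quantify the relationship between renal function, as measured by eGFR, and TC-5214 dose-normalized primary pharmacokinetic parameters", and names these as Cmax and AUC. The exploratory one-way analysis of variance against Group 1 and the paired t-test in Group 5 Part 1 use the same two parameters.

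Section 11.2 derives CL_R as a urine parameter, Ae(0-t) divided by AUC(0-t). It derives dialysate clearance (CL_D) from dialysate over 4-8 h (Group 5 Part 1, Period 2) and over 72-76 h (Group 5 Part 2). Under the synopsis and Section 12.2.1, derived PK parameters receive descriptive statistics by renal function group, including the geometric mean and geometric CV%.

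The synopsis outcome list gives a different assignment: "Ae, CL_D, and fe in Groups 1 to 4; A_{d(4-8)}, Cl_R, and fd₍₄₋₈₎ in Group 5 during Period 2".

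**The concern.** The trial spends substantial effort on measuring renal excretion. Urine is collected for 72 h in Part 1 and 120 h in Part 2, and the amendment's rationale for adding Group 5 urine is that renal clearance can then be calculated. The analysis section does not put the result into any model. A reader of the report would get group summaries of CL_R. The report would not say how much CL_R changes per unit of eGFR, or give an interval for the ratio of each impaired group to controls.

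CL_R also has properties that the modelled AUC lacks. It needs no extrapolation to infinity. It also needs no normalization between the 8 mg groups and the 2 mg groups. A straight line in eGFR, the plan's starting model, is a natural form for a clearance.

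The synopsis list adds a separate inconsistency: as written there, neither clearance could be calculated in the subjects to whom it is assigned.

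**Working it through.** **1. Response variables of the planned analyses (Synopsis and Section 12.2.3)**

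| Analysis | Response | CL_R included? |
|---|---|---|
| Regression on eGFR | Cmax, AUC | No |
| One-way ANOVA against Group 1 | Cmax, AUC | No |
| Paired t-test, Group 5 Part 1 | Cmax, AUC | No |
| Descriptive summary by group | All derived PK parameters | Yes |

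CL_R is therefore the response in 0 of 3 modelled analyses, but it is included in the descriptive summary.

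**2. Who can supply CL_R**

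- Section 6.4.1.3: "For Part 1, urine will be collected in Groups 1 through 3 from predose to 72 hours postdose". The footnote to Table 1 agrees: "Urine collection times for Groups 1 to 3: Urine will be collected for 72 hours postdose". Group 5 Part 1 therefore supplies none.
- In Part 2, urine comes from Groups 1 to 3 and from Group 5 subjects able to produce it.
- Groups 1 to 3: 8 + 8 + 8 = 24 planned subjects.
- Group 5: 8 planned, of whom the first 4 are in Part 1, leaving 8 − 4 = 4 in Part 2. Between 0 and 4 of these produce urine.
- Total: 24 to 28 of the 32 planned subjects.

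**3. Where avoiding extrapolation matters**

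Section 11.2 does not report AUC if more than 30% is extrapolated. Section 3.2 gives a usual half-life of about 8 to 9 h, increased about 3-fold in moderate impairment and 10-fold in ESRD (2 subjects each). The implied half-lives are 24 to 27 h and 80 to 90 h.

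Assume mono-exponential decline, and ignore absorption and dialysis. The extrapolated share is then 2^(−t/T), where t is the last sampling time and T the half-life.

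| Subjects | T (h) | t = 72 h | t = 120 h |
|---|---|---|---|
| Moderate | 24 to 27 | 12.5% to 15.7% | 3.1% to 4.6% |
| ESRD | 80 to 90 | 53.6% to 57.4% | 35.4% to 39.7% |

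The 30% limit is reached when t/T = log2(1/0.30) = 1.737. That is T = 72/1.737 = 41.5 h for sampling to 72 h, and T = 120/1.737 = 69.1 h for sampling to 120 h. The interim ESRD half-life exceeds both. In Part 2 the dialysis session at about 72 h would lower the 120 h figure by an amount that the documents do not give.

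On these figures the rule threatens AUC in Group 5 and not in Groups 1 to 3. Freedom from extrapolation therefore helps directly only in the 0 to 4 urine-producing subjects of Group 5 Part 2.

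**4. Synopsis list against the body**

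- CL_D is listed for Groups 1 to 4. Section 3.1 says "Subjects in Groups 1 through 3 will not be on dialysis", and Group 4 is no longer recruited.
- CL_R is listed for Group 5 in Period 2. Only Part 1 of Group 5 has a Period 2, and step 2 shows that no urine is collected there.
- The 72-76 h dialysate parameters of Part 2, derived in Section 11.2, are missing.

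Exchanging the two clearance symbols restores agreement with Section 11.2, apart from the outdated group number and the missing Part 2 entries.

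**The case against.** A reader might infer that the trial leaves its hypothesis without an answer. The documents do not support that. The hypothesis concerns plasma pharmacokinetics and ends in increased exposure, with reduced renal clearance as the proposed route. AUC and Cmax are the primary parameters, and they are modelled against eGFR and compared with controls. Nor is it true that CL_R goes unestimated: group geometric means, including the control group's, are planned.

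The AUC regression also carries much of the same information. Dose-normalized AUC is the reciprocal of CL/F, and Section 1.3 reports 89.5% to 93.9% of the dose as parent drug in urine with very little non-renal clearance. A CL_R model would be largely confirmatory. The study is declared exploratory, with no formal testing and with intervals for description only. No separate SAP is shown, and models for secondary parameters are often left to that document.

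These points stand, and they make the addition supportive rather than a repair of the primary analysis. They do not remove its value. Section 12.2.3 specifies which parameters are modelled, the parameter is already derived, and an interval on the mechanism costs almost nothing.

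A reader might also infer that the synopsis fault would stop CL_R from being computed. It would not: the abbreviations list defines both clearances correctly, and Section 11.2 gives a workable derivation for each. The fault is editorial.

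**Conclusion.** The point holds in a limited form. The exposure part of the hypothesis is modelled. The mechanism part gets descriptive summaries only, without a slope on eGFR or a 90% CI for the ratio to controls. The affected values number 24 to 28; 28 is a ceiling that requires every Group 5 Part 2 subject to produce urine. Nothing here bears on error rates or sample size, since the plan has no formal testing and no formal sample size calculation.

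The robustness argument rests on interim half-lives from 2 moderate and 2 ESRD subjects and on a mono-exponential approximation that ignores dialysis. It supports CL_R as a useful second view at the low end of eGFR. It does not make CL_R a substitute for AUC in ESRD. Group 5 Part 1 supplies no CL_R, and any Part 2 contributors are selected for still producing urine.

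The synopsis transposition is a real inconsistency in the current text, but of minor consequence.

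**What to change.** **Section 12.2.3.** Add CL_R = Ae(0-t)/AUC(0-t), without dose normalization, as a supportive secondary response in two places:

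- the eGFR regression, starting from a straight line, reporting the slope and 90% CI;
- the comparison with Group 1, reporting ratios and 90% CI.

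Use Groups 1 to 3 plus any Group 5 Part 2 subjects who produce urine. State that the urine and plasma intervals must match for each subject, and report how many Group 5 subjects contribute.

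**Synopsis, outcome variables.** Align with Section 11.2:

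- list CL_R with Ae and fe for the subjects whose urine is collected;
- list CL_D with Ad and fd for the Group 5 dialysis sessions, over 4-8 h in Part 1 Period 2 and 72-76 h in Part 2;
- delete the reference to Group 4.

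The cost is one further model on a parameter already derived and a corrected list. No new samples or visits are needed.
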